12.3.2 Primary outcome analysis

The primary outcome is the time to the next exacerbation within the 90-day study period. This will be analysed using Cox proportional hazards regression and the estimated hazard ratio between the groups will be reported, along with its standard error. A log-rank test will be used to test the primary hypothesis. A Kaplan-Meier plot will be produced. Patients who do not suffer a recurrent exacerbation during follow-up will be treated as censored observations at their end of follow-up time. As analysis is intention to treat, non-compliers will be treated as belonging to the treatment group originally randomised to. Where patients withdraw from follow up, every effort will be made

to ascertain their primary outcome (i.e. date of next exacerbation OR exacerbation-free survival to 90 days) by telephone.

Analysis will be adjusted for a number of important baseline covariates including; sex, exacerbation phenotype, level of symptoms (CAT), levels of CRP, disease severity (FEV), baseline exacerbation frequency in previous year, hospital admission at initial exacerbation.

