12.3.3 Secondary outcome analysis

Summary measures of the secondary endpoints will be presented (mean, standard deviation, median, interquartile range for continuous variables, percentages for categorical variables) by treatment group and for both baseline and end of trial follow-up visits. The percentage of missing data will be summarised.

- Time until resolution of first exacerbation will be compared between the active treatment and placebo groups, using a log-rank test. Cox regression analysis will also be conducted adjusting for important baseline covariates.
- The number of treatment-related adverse events will be analysed by using (over dispersed) Poisson regression or a suitable zero-inflated model and adjusted for treatment group and important baseline covariates.
- Exacerbation frequency: The rate of exacerbations experienced during the study period will be analysed by using (over dispersed) Poisson regression or a suitable zero-inflated model and adjusted for treatment group and important baseline covariates and with length of follow-up as an offset.
- Frequency of antibiotic courses: The rate of antibiotic courses received for patients in the active treatment and placebo groups will be compared using (over dispersed) Poisson regression or a suitable zero-inflated model adjusting for treatment group and important baseline covariates.
- The rate of hospital attendances during the study period will be analysed by using (over-dispersed) Poisson regression or a suitable zero-inflated model and adjusted for treatment group and important baseline covariates.
- Changes in respiratory healthcare status, assessed using SGRQ and CAT. SGRQ (score between 0 and 100) and CAT (score between 0 and 40) from baseline to day 90 will be modelled as a normally distributed random variable by using a suitable transformation (e.g. a Box-Cox like transformation to remove skewness and possible boundary effects). Any analysis will be adjusted for baseline scores, treatment, and other important baseline covariates. Repeated measures analysis will be used to assess treatment effects over time during the follow-up period.

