The primary outcome is the time to the next exacerbation within the 90-day study period. This will analysed using Cox proportional hazards regression, stratified by centre. The estimated hazard ratio between the groups will be reported, along with its 95% CI. A Kaplan-Meier plot will be produced. Patients who do not suffer a recurrent exacerbation during follow-up will be treated as censored observations at their end of follow-up time. As analysis is intention to treat, non-compliers will be

treated as belonging to the treatment group originally randomised to. Where patients withdraw from follow up, every effort will be made to ascertain their primary outcome (i.e. date of next exacerbation OR exacerbation-free survival to 90 days) by telephone. We will adjust only for number of exacerbations in previous year and centre in this primary analysis.

Variables:

Time until event or censoring: excn.or.cens.d
 surv1 <- coxph(Surv(time, cens) ~ arm

A supporting analysis will be undertaken that adjusts for site and patient selfreported history of exacerbations in the previous year.

- o **site:** site
- Excns in previous year: prev.excns
- Arm: [not yet released]

surv1 <- coxph(Surv(time, cens) ~ arm + strata(site) + prev.excns)</pre>

An additional supporting analysis will be undertaken, additionally adjusting for baseline covariates age; sex; FEV1% predicted; SGRQ total score; number of exacerbations in previous year; whether hospitalised for index exacerbation; whether index exacerbation was treated with steroids in addition to antibiotics; whether included due to symptomatic or inflammatory criteria, and smoking status. This will be for hypothesis generation only. It will not be used to come to overall conclusions regarding treatment efficacy; this will be treated as a secondary analysis.

- Age (continuous): *age.cts*
- Sex: sex
- FEV1% predicted at baseline: fev.pred
- SGRQ total score at baseline: *sgrq1.total*
- **Hospitalised for index excn (y/n):** *hospital.yn*
- Index excn treated with steroids (y/n): *steroids.given.yn*
- Included due to symptomatic criteria or inflammatory criteria [to be queried]
- Smoking status: curr.smok

surv2 <- coxph(Surv(time, cens) ~ arm + strata(site) + prev.excns + age.cts + sex + fev.pred +
sgrq1.total + hospital.yn + steroids.given.yn + XXX[inclusion crit.] + curr.smok, data=wp4)</pre>

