The percentage of missing data will be summarised and spurious data double checked as far as possible. Primary analysis will be intention to treat, and so every effort will be made to collect all follow-up data from non-compliers and patients who discontinue treatment. All patients will be analysed from the date of randomisation until end of follow-up period or the date of drop-out. The primary analysis will therefore assume patients who drop-out of the trial do so 'at random'.

Secondary outcome analysis

For each secondary outcome, two analyses will be undertaken – the first adjusting for centre and the baseline value of the endpoint being analysed (where available), and the second also taking into account the additional baseline characteristics specified in the supporting analysis of the primary outcome above.

When modelling continuous data, transformations will be undertaken as necessary to normalise the data. Where appropriate, analyses will take account of length of follow up as an offset, and also account for differences in at-risk periods. Summary measures of the secondary outcomes will be presented (mean, standard deviation, median, interquartile range for continuous variables, percentages for categorical variables) by treatment group and for both baseline and end of trial follow-up visits. The percentage of missing data will be summarised.

Secondary outcomes

- Time until *resolution* of first exacerbation will be compared between the active treatment and placebo groups, using Cox proportional hazards regression, stratified by centre.

• Duration of first exacerbation: dur

- The number of treatment-related adverse events will be analysed by using negative binomial regression. Negative binomial regression models collapse to Poisson regression if there is no overdispersion.

• Number of treatment-related AEs: trt.rltd.aes

- Exacerbation frequency: The rate of exacerbations experienced during the study period per person-year will be analysed by using negative binomial regression.

• Number of exacerbations: excns

- Frequency of antibiotic courses: The rate of antibiotic courses received for patients in the active treatment and placebo groups will be compared using negative binomial regression.

- The rate of hospital attendances during the study period will be analysed by negative binomial regression. .

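### Time to resolution of the index exacerbation is never adjusted for day-0 CAT, and the first-level models for resolution, antibiotic courses and hospital attendances adjust for centre only

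*SAP*

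**What the plan says.** SAP, Secondary outcome analysis, sets two models for each secondary outcome: "the first adjusting for centre and the baseline value of the endpoint being analysed (where available"). A fuller model then keeps those terms and brings in the covariates of the primary outcome's supporting analysis. That set is in SAP, Primary outcome analysis: "additionally adjusting for baseline covariates age; sex; FEV1% predicted; SGRQ total score; number of exacerbations in previous year", then hospitalisation and steroids for the index exacerbation, inclusion criterion and smoking status. CAT is not in it.

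For time to resolution, SAP, Secondary outcomes, specifies a comparison "between the active treatment and placebo groups, using Cox proportional hazards regression, stratified by centre". Antibiotic courses and hospital attendances are given negative binomial regression with no covariate named. For the primary outcome, by contrast, the SAP says "We will adjust only for number of exacerbations in previous year and centre in this primary analysis".

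Protocol 12.3.2 lists the important covariates for the primary outcome, among them "level of symptoms (CAT), levels of CRP, disease severity (FEV), baseline exacerbation frequency in previous year". For time to resolution, Protocol 12.3.3 plans a log-rank test and adds: "Cox regression analysis will also be conducted adjusting for important baseline covariates". It also adjusts the antibiotic and hospital rates for important baseline covariates, without listing them again. Both documents say the secondary outcomes are not powered and are hypothesis generating only.

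**The concern.** A rule that relies on the endpoint's own baseline value gives no covariate when there is no such value. A time to resolution, a count of antibiotic courses after day 0 and a count of hospital attendances after day 0 are in that position. Yet the trial records two plausible predictors at V1: the CAT score, a 0 to 40 symptom measure, and the number of exacerbations in the previous year.

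The gap is widest for time to resolution, because CAT is missing from both planned analyses. The second analysis has SGRQ instead. Under Protocol 8.4 the V1 SGRQ looks back 4 weeks, while treatment of the index exacerbation began about 14 days earlier, so its window spans the exacerbation itself. Resolution is defined by symptom-free diary days (Protocol 12.1.2), which makes a day-0 symptom score a natural adjustment variable.

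In a Cox model, leaving out a prognostic covariate moves the estimated hazard ratio towards 1 and reduces power, even when randomisation has balanced the covariate. Faster recovery is one of the two effects named in the programme aim (Protocol 3.1), so a diluted estimate would be a poor guide to later work.

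**Working it through.** **1. Which covariate is in which model**

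| Outcome | First analysis | Second analysis adds |
|---|---|---|
| Time to resolution | centre | prior-year exacerbations, SGRQ, inclusion criterion and the rest; not CAT |
| Antibiotic courses | centre | the same set |
| Hospital attendances | centre | the same set |

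V1 CAT is completed before the study drug is dispensed (Protocol 8.4). Prior-year exacerbations are recorded at V1 and are already in the database as `prev.excns`.

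**2. The plan's own figure**

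The SAP states power for the primary outcome only: N = 138, 5% dropout, 80% power at HR 0.46 and 90% at HR 0.39, from 45% exacerbation-free at 90 days. The 5% two-sided level is in Protocol 12.2.1.

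- Evaluable: 138 × 0.95 = 131.1.
- Events = 131.1 × [0.55 + (1 − 0.45^HR)] / 2, which is 56.2 at HR 0.46 and 53.6 at HR 0.39.
- Freedman: power = Φ(√events × (1 − HR)/(1 + HR) − 1.96).
- HR 0.46: √56.2 × 0.54/1.46 − 1.96 = 0.81, so 79.2%.
- HR 0.39: √53.6 × 0.61/1.39 − 1.96 = 1.25, so 89.5%.

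The stated figures reproduce. They do not bear on the secondary models, for which the documents give no effect size, event rate or strength of association. Everything below is therefore conditional on assumed inputs.

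**3. Time to resolution, simulated**

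The hazard of resolution is multiplied by HR in the ciprofloxacin arm (HR above 1 means faster recovery) and by exp(−g) for each SD of the baseline covariate. There are 131 patients, followed to day 90. The figures are power without and with the covariate.

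*HR 1.5, placebo median 10 to 20 days:*

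| g per SD | 1,500 runs per setting | 1,200 runs per setting |
|---|---|---|
| 0 | 58–60% either way | 61% vs 61–62% |
| 0.3 | about 55% vs 60–63% | 56–58% vs 60–63% |
| 0.5 | 44–47% vs 58–60% | 49–51% vs 62–64% |

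At g = 0.5 the hazard ratio without the covariate falls from 1.5 to about 1.4.

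*HR 1.65, 80% of controls resolved by day 90, four sites, Cox stratified by site, 400 runs (Monte Carlo error about 2 points):*

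| g per SD | Centre only | Centre + covariate | Estimated HR |
|---|---|---|---|
| 0 | 72% | 72% | 1.66 vs 1.67 |
| 0.2 | 70% | 76% | 1.64 vs 1.67 |
| 0.4 | 66% | 73% | 1.56 vs 1.65 |
| 0.6 | 58% | 72% | 1.53 vs 1.65 |

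For g from 0.3 to 0.6 the loss is about 5 to 14 points. At g = 0 it is nil.

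**4. The two rates, simulated** (negative binomial with site terms, without vs with the covariate)

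- Antibiotic-type rate, mean 1.0, rate ratio 0.55, dispersion 0.5. For g = 0, 0.2, 0.4, 0.6: 71% vs 71%, 65% vs 67%, 63% vs 67%, 61% vs 71%.
- Hospital-type rate, mean 0.3, rate ratio 0.40. The gain is about 1 point or less at every g. About 30% of these fits failed to converge, so this result is rough. A mean of 0.3 is in line with the figure of up to 30% readmitted within 90 days in Protocol 10.4.

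**5. What was not compared**

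These runs set CAT against no covariate. None sets CAT against a model that already holds SGRQ and the inclusion criterion.

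**The case against.** The strongest reply is that the plan already has a second, fuller analysis of every secondary outcome. A reader might infer from the centre-only models that the SAP ignores prior exacerbations for the rates, or that a chance imbalance in them would be corrected for the primary outcome and left uncorrected here. The documents do not support that: the second analysis of each rate includes prior-year exacerbations. One qualification is that the inclusion-criterion variable in that set is still a placeholder to be queried, so the second model cannot be run exactly as written.

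Other parts of the reply also stand:

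- Protocol 12.3.2 lists covariates for the primary outcome. Protocol 12.3.3 does not name CAT for resolution, and it puts an unadjusted log-rank test beside the adjusted Cox model. A light model followed by a fuller one keeps that structure.
- No passage shows that CAT predicts resolution.
- The SAP is not settled on its own primary model. One sentence adjusts for prior exacerbations and centre, the first code line has treatment arm alone, and the adjusted model is then called supporting. The precedent for `prev.excns` is therefore weaker than that sentence suggests.
- Adjustment is not free. It changes the hazard ratio being estimated to one conditional on CAT, and patients without a CAT score could drop out of the model.

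What the reply does not answer is that CAT is in neither analysis of time to resolution.

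**Conclusion.** The point holds in a limited form. For these three outcomes the first analysis adjusts for centre only, and V1 CAT is absent from both analyses of time to resolution. If CAT is prognostic at 0.3 to 0.6 log hazard ratio per SD, the centre-only model loses about 5 to 14 points of power, assuming 131 evaluable patients and a true HR of 1.5 to 1.65. With no association it loses nothing. For antibiotic courses the corresponding loss is 0 to 10 points. For hospital attendances no power gain can be claimed.

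A reader might conclude that the SAP certainly wastes power and gains nothing in return. That goes too far. The association is assumed, the benefit of CAT beyond the second-level model is unmeasured, and adjustment has the small costs named above. The outcomes are declared unpowered and hypothesis generating, so no main conclusion of the trial depends on this. Severity is low, and the case for change rests on how little it costs.

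**What to change.** In SAP, Secondary outcome analysis, name the first-level models for outcomes that have no baseline value of their own:

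- Time until resolution: Cox with `arm + strata(site)` + V1 CAT total score.
- Antibiotic courses: negative binomial with `arm + site + prev.excns`.
- Hospital attendances: the same terms, for consistency with the stated primary adjustment and with no power gain claimed.
- Exacerbation rate: state that `prev.excns` is its baseline value.

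State that the resolution hazard ratio is conditional on CAT, and give a rule for missing V1 CAT that keeps every randomised patient in the model (for example, imputing the overall baseline mean). It would also help to say which of the two analyses of each secondary outcome leads.

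The cost is SAP wording and one degree of freedom per model, with no new data. The SAP lists the arm variable as not yet released, so on its own account the change can be made before unblinding.

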12.2 Sample size and recruitment

12.2.1 Sample size calculation

Over the two centres, based on HES data, we anticipate that a total of 218 hospital admission or ambulatory exacerbations will be identified over the 18-month recruitment period (<http://www.hscic.gov.uk/hes>). Based on data from the London COPD Cohort, 33% of exacerbating patients have a CRP of 8 or above at 2 weeks. Furthermore, our pilot data suggest that of patients with CRP >8mg/L, at least 60% of patients report symptoms at day 14. Thus, assuming that 90% of eligible patients will agree to take part in the study, we expect $218/3 \approx 73$ patients eligible due to CRP level, $0.6(218-73) = 87$ eligible due to symptoms at day 14, and to randomise $0.9(73+87)=144$ patients in total.

Pilot data from our group suggests that at a level of CRP>10mg/l at 14 days, there will be 36% recurrent exacerbations within 50 days. Assuming a constant hazard of exacerbation this translates to around a 55% recurrent exacerbation rate at 90 days. A similar proportion of recurrent exacerbations are seen in the London COPD cohort (for both CRP>10 and CRP<10). An observational database study by Roede et al. (2008) reported a hazard ratio of 0.62 when antibiotics were given in addition to usual treatment. Allowing for a 5% dropout, we will therefore have 80% power at a 5% two-sided significance level to detect a 22% absolute reduction in the proportion of exacerbations seen at 90 days (from 55% to 32%), using time-to-event (survival) methods. This is equivalent to detecting a hazard ratio of 0.48 over the follow-up period.

The recruitment period for this trial is estimated to be 18 months, requiring approximately 8 patients per month to be randomised across both sites.

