
- Post-bronchodilator spirometry: Specifically the measurement of volume and flow of air inhaled and exhaled. The parameters measured will be the Forced vital

capacity (FVC) and Forced expiratory volume (FEV) at 1 second. The FEV1/FVC ratio and FEV1 as a percentage of predicted normal value will be computed to assess FEV1 and FVC. A minimum of three spirometry readings will be taken to assess FEV1 and FVC. The highest individual FEV1 and FVC readings will be used to calculate the FEV1/FVC ratio and for comparison with the predicted normal value. This will be taken at screening visit (V1), first follow up (V2), second follow up (V3), end of study (V4) and if patient presents with exacerbation during study (EX).

The spirometry will be considered post-bronchodilator if the patient has taken their usual long-acting bronchodilator medication OR if they have had a shortacting bronchodilator administered in clinic 10-15 minutes prior to spirometry testing.

- Diary Cards: These cards will be used to measure changes in symptoms/side effects, as well as in defining exacerbations for the primary endpoint, and therefore will be carefully explained to the patient at this time, and at every visit (as spirometry).
- General baseline characteristics: Age, gender, smoking status, self-reported exacerbation frequency in the previous year, Smoking history (pack years)
- Basic physiological measurements and clinical examination: These include blood pressure, oxygen saturations, pulse oximetry, respiratory rate, pulse rate, height, weight, BMI and a full clinical exam. These will all be performed in the usual manner, and measured at V1 and at exacerbation visit (EX).
- Pill count: This will be taken at V2.
- CRP Blood samples: Will be collected and analysed for CRP levels to measure presence of inflammation in the body. This is measured in milligrams per litre of blood (mg/L), and will be measured at every visit (as spirometry).
- Serum samples: will be taken at every visit (as spirometry) and stored at -80C for future analysis of inflammatory markers.
- Sputum samples: If spontaneously expectorated, the sputum samples will be collected and analysed to measure bacterial load in the lung. Concentrations will be log transformed and expressed as log10 CFU (colony forming units)/ml. Collection of sputum is not a requirement for study entry and this will therefore form a subgroup analysis. The sputum samples will be collected from patients at

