Due to relocation from the Royal Free Hospital to the Royal Brompton Hospital, a more realistic sample size of 138 is now expected. We do not anticipate a change in the expected proportion of exacerbation-free survival at 90 days of 0.45, and we still allow for 5% dropout. This would result in:

- 90% power to detect a HR of 0.39 an increase in survival at 90 days from 0.45 to 0.73;
- 80% power to detect a HR of 0.46 an increase in survival at 90 days from 0.45 to 0.70.

The recruitment period for this trial is estimated to be 18 months, requiring approximately 20 exacerbations per month to be identified across both sites. It is likely that 2/3 of these will come from RFH and 1/3 from UHA.

Statistical Analysis Plan

Timing of Analyses

• Recruitment of the 138 patients began in the London site in July 2014, and should commence shortly at the Liverpool site.

• Data for completed patients should begin to become available in October 2014.

Descriptive analyses

(i) Should include CONSORT diagram describing patient flow with exclusions (including reasons for exclusions) and total numbers randomised to each treatment arm. This will include attendance at each visit and loss to follow-up (including follow-up time).

(ii) Baseline comparability of randomised groups:

- By December 2015 (approximately), recruitment should be completed, at which point tables of summary statistics will be produced. These tables will include (but are not limited to) the following baseline variables; age (continuous), sex, BMI, smoking status, smoking pack year history, centre, bacterial load, CRP (from blood sample), spirometry measurements, exacerbation history (number experienced in previous year) and questionnaire scores for each randomised group.
- Continuous variables will be summarised using the following statistics; n (nonmissing sample size), mean, standard deviation, median, inter-quartile range, maximum and minimum. The number of missing observations will also be reported.
- The frequency and percentages (based on the non-missing sample size) of observed levels will be reported for all categorical measures. The number of missing observations will also be reported.

Primary outcome analysis

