- Changes in respiratory healthcare status, assessed using SGRQ. SGRQ (score between 0 and 100from baseline to day 90 will be modelled as a normally distributed random variable. Linear regression will be used,

- Changes in respiratory healthcare status, assessed using CAT. CAT (score between 0 and 40) from baseline to day 90 will be modelled as a normally distributed random variable. Repeated measures analysis will be used to assess treatment effects over time during the follow-up period.

- Lung function: Changes in FEV1, FEV1 as % predicted, and FEV1/FVC ratio and FVC at day 90 from day 0 will be modelled separately as continuous outcomes and assumed to be normally distributed. Repeated measures analysis will be used to assess treatment effects over time during the follow-up period.

- Change in CRP from study entry to 90 days will be modelled as a normally distributed random variable. Repeated measures analysis will be used to assess treatment effects over time during the follow-up period.

- Resistance patterns (not resistant, resistant) will be analysed using logistic regression.

- The change in (log10) bacterial load from trial beginning to end will be analysed using parametric survival regression(linear regression with censored outcome data). Values below limits of detection will be treated as left censored.

- Adherence as assessed by pill counts. The number of pills taken over total number dispensed will be modelled using logistic. The difference in percent adherence will be assessed between treatment groups.

- Cost-effectiveness will be assessed as part of a future study (WP5)

This study is not powered to test these secondary outcomes – only the primary outcome. As such, analyses of the secondary outcomes will be hypothesis generating only.

Subgroup analyses

Relevant subgroups may be analysed (including patients who gave sputum samples), allowing the incorporation of any important new information and methodological concerns identified between now and the time of writing the analysis plan. However, such analyses should be undertaken before unblinding, and keeping in mind that any analyses will be hypothesis generating only.

Sensitivity analysis

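### With four sites, the SAP's fully adjusted logistic model for ciprofloxacin resistance has 14 terms and, at best, fewer than five patients in the rarer category per term

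*SAP*

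**What the plan says.** The SAP (Secondary outcome analysis) sets two analyses for each secondary outcome. The first adjusts for centre and, where available, the baseline value of the endpoint. The description of the other reads: "the second also taking into account the additional baseline characteristics specified in the supporting analysis of the primary outcome above". That supporting analysis (SAP, Primary outcome analysis) lists nine covariates: previous-year exacerbations, age, sex, FEV1 % predicted, SGRQ total, hospitalisation for the index exacerbation, steroid treatment of it, inclusion criterion and smoking status.

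Under Secondary outcomes the SAP states: "Resistance patterns (not resistant, resistant) will be analysed using logistic regression". It gives no exemption from the second model, no minimum count and no method for sparse data. On sputum it says (Study variables and endpoints): "Collection of sputum is not a requirement for study entry and this will therefore form a subgroup analysis". Protocol 12.1.2 assesses resistance at the beginning and end of the trial in patients who expectorate spontaneously, so a model adjusted for baseline resistance needs two samples per patient. Protocol 12.3.3 also adjusts resistance for baseline values and other important covariates. The SAP declares all secondary analyses hypothesis generating.

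**The concern.** The blanket rule takes a covariate set written for a time-to-event analysis of the whole trial and applies it to a binary outcome in a subset. Maximum-likelihood logistic regression with many terms and few patients in the rarer category overfits. When the data separate, it returns an arbitrarily large or undefined odds ratio. Resistance is a named secondary objective (Protocol 4.2), and limiting resistance is part of the programme's stated aim (Protocol 3.1). An unstable odds ratio could alarm or reassure for no good reason. With no fallback written down, the analyst would have to choose one after seeing the data.

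**Working it through.** **1. Number of patients.** The SAP (Sample size) says "a more realistic sample size of 138 is now expected" and "we still allow for 5% dropout": 138 × 0.95 = 131.1 followed.

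The SAP's own power figures confirm this base. Events = 131.1/2 × [0.55 + (1 − S)], where S is 90-day survival on treatment. Freedman log-rank power = Φ(√events × (1 − HR)/(1 + HR) − 1.96). The 5% two-sided level comes from Protocol 12.2.1; the SAP does not restate it.

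- "80% power to detect a HR of 0.46 an increase in survival at 90 days from 0.45 to 0.70": 131.1/2 × 0.85 = 55.7 events, power 78.8%.
- "90% power to detect a HR of 0.39 an increase in survival at 90 days from 0.45 to 0.73": 131.1/2 × 0.82 = 53.8 events, power 89.6%.

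Both agree within 2 percentage points (Schoenfeld's formula gives 82.6% and 93.2%). Neither document states any figure for the resistance model.

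**2. Terms in the second resistance model, excluding the intercept.** Arm 1 + centre 3 + baseline resistance 1 + nine covariates = 14. The SAP's Background speaks of two hospitals but names four; with two sites the count is 12. The coding of the inclusion criterion is still open in the SAP; three levels would make 15 with four sites. The first model has arm 1 + centre 3 + baseline 1 = 5.

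**3. A bound that needs no assumed rate.** The rarer category cannot exceed half the patients: 131/2 = 65.5.

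- 14 terms: 65.5/14 = 4.7 per term. With the protocol's 144 patients: 144 × 0.95/2/14 = 4.9.
- 12 terms: 65.5/12 = 5.5 per term.
- First model: 65.5/5 = 13.1 per term.

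**4. Assumed range.** Sputum share and resistance rate are assumptions. Rarer category = 131 × share × rate.

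| Sputum share / resistant | Patients in rarer category | Per term, 14 terms | Per term, 5 terms |
|---|---|---|---|
| 70% / 30% | 27.5 | 2.0 | 5.5 |
| 50% / 20% | 13.1 | 0.9 | 2.6 |
| 60% / 10% | 7.9 | 0.6 | 1.6 |
| 30% / 5% | 2.0 | 0.1 | 0.4 |

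**5. Simulation with no true arm effect.** Divergence means that the arm coefficient or its standard error exceeds 5 in absolute value. Ranges cover repeated sets of runs; the covariate distributions are assumptions.

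| Pairs / resistant | Expected resistant | Arm OR diverges, 14 terms | Arm OR diverges, first model |
|---|---|---|---|
| 50 / 10% | 5 | 62–82% | 21–22% |
| 50 / 20% | 10 | 20–43% | 2–3% |
| 80 / 10% | 8 | 18–34% | 4–8% |
| 65 / 20% | 13 | 5% | 0% |

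At 80 pairs with 20% resistant, and in the larger settings tried (92 with 30%, 131 with 20%), the 14-term arm estimate diverged in 0–2%.

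**6. Does removing the covariates suffice?** Not entirely. Counting separation on any term (65 pairs, 10% resistant), the 14-term model separates in 74% of data sets and the 5-term model in 71%, because sparse centre and baseline cells drive much of it. Separation on a centre term need not spoil the arm estimate, but the first model's arm estimate still diverges in about a fifth of trials in the sparsest setting. Firth penalisation removed divergence with or without centre. It does not create information: a two-term Firth model still gave an odds ratio above 3 or below 1/3 in 28% of trials at 50 pairs and 10%.

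**The case against.** The strongest reply is that the SAP already contains a much more stable resistance estimate, the first analysis. It also requires summary percentages by treatment group, calls all secondary results hypothesis generating, and allows justified deviations. Divergence shows itself through a huge standard error or a software warning. In simulation, a non-divergent nominally significant arm effect appeared in only 0–8% of trials. All of this stands and keeps the point small. It does not justify a prescribed model that is overfitted at any resistance rate, or leaving the fallback until after the data are seen.

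Stronger readings that a reader might infer are not supported:

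- *Every secondary outcome gets about 14 terms.* Counts run from 10 to 14. Time to resolution has 10 (Cox model stratified by centre, no baseline value). SGRQ and FEV1 % predicted have 13, because their baseline is already a covariate. Several outcomes are continuous, where 13 or 14 terms in about 131 patients is unremarkable.
- *There will be too few resistant patients to fit the model.* The documents give neither sputum yield nor resistance rate. At the high end the model can be fitted, though imprecisely.
- *All binary and count secondaries need ten events per term.* That rule of thumb is contestable. A 13-term count model would need 130 events, while the SAP's assumptions imply about 56 first exacerbations, so the rule could remove several planned analyses without a demonstrated need.

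**Conclusion.** The point holds for the second resistance model alone. With four sites it has 14 terms and cannot exceed 4.7 patients in the rarer category per term (5.5 with two sites and 12 terms). That ceiling rests only on the SAP's sample size, dropout allowance and covariate list, with each covariate entered as one term.

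Whether the model actually fails depends on rates that the documents do not give. With 50 to 80 pairs and 10% resistant, its arm odds ratio diverges in roughly 20–80% of null trials, against about 4–22% for the first model. From about 80 pairs and 20% resistant upwards, failure is rare (about 0–2%) and the defect is mainly overfitting. It is a modest point about one exploratory analysis, worth correcting because the correction is cheap. It does not touch the primary conclusion.

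**What to change.** Add one sentence to the SAP under Secondary outcomes: the second, fully adjusted analysis is not run for resistance; resistance is analysed with the first model only (arm, centre, baseline resistance), fitted by Firth-penalised logistic regression, and reported beside the number resistant out of the number with paired samples in each arm. Keep centre, since randomisation is stratified by site. Record the change before the allocation is released, and note that it departs from the wider covariate adjustment in Protocol 12.3.3.

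The cost is that one exploratory adjusted model is dropped. The penalised estimate may still be imprecise, which is why the counts belong next to it. No general events-per-term rule is needed for the other secondary outcomes.
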